[name]

**A PHASE 3 STUDY TO EVALUATE THE IMMUNOGENICITY AND SAFETY OF
NOVAVAX COVID-19 VACCINE(S) AS SECOND OR SUBSEQUENT BOOSTERS
AFTER mRNA VACCINES IN INDIVIDUALS 18 TO 49 YEARS OF AGE**

Novavax Protocol Number: 2019nCoV-312

**STATISTICAL ANALYSIS PLAN (SAP) FOR
Interim/Final Analysis of Immunogenicity and Safety Data**

SAP Version and Date: Version 4.0 –22AUG2023

- Ancestral strain NVX-CoV2373 (5 µg)

Investigational Product:

- Updated Novavax COVID-19 vaccine based on recent variant(s)

Confidentiality Statement

The information contained herein is confidential and the proprietary property of Novavax, Inc. and any unauthorized use or disclosure of such information without the prior written authorization of Novavax, Inc. is expressly prohibited.

APPROVAL SIGNATURE PAGE

Protocol Number:	2019nCoV-312
Protocol Version and Date:	Version 2.0 (Amendment 1.0) – 23 February 2023
Protocol Title:	A phase 3 study to evaluate the immunogenicity and safety of Novavax COVID-19 vaccine(s) as second or subsequent booster after mRNA vaccines in individuals 18 to 49 years of age
SAP Version and Date:	Version 4.0 – 22 AUG 2023

Original Statistical Analysis Plan
 Amended Statistical Analysis Plan

SAP Originated By:

[figure not shown]
A large black rectangular box redacting a signature.

22 August 2023

[figure not shown]
Date

Signatures below indicate the SAP has been reviewed and approved by the following personnel:

[figure not shown]
Signed Electronically

Signed Electronically

Signed Electronically

SAP CHANGE HISTORY

SAP Version 3.0, 16 May 2023 (revised from Version 2.0, 03 March 2023)

The following is a summary of the changes made to this SAP.

Location of Change	Change/Modification in Version 3.0
Section 3.2, Section 3.5, Section 4 and Section 5	Remove the analysis per FAS due to the change of enrollment procedure, that is, subjects to be dosed with ancestral strain NVX-CoV2373 are enrolled first and subjects to be dosed with updated Novavax COVID-19 Vaccine based on recent variant(s) are enrolled afterward.
Section 7.2.1	Clarify SCR definition for Nab titers per CBER comments: SCR is defined as proportion of participants who achieve seroconversion \geq 4-fold increase from baseline in Nab titers at Day 29 if the baseline value is equal to or above LLOQ or at least 4-fold fold rise from LLOQ if the baseline value is lower than LLOQ
Section 7.2.2	Clarify SCR definition for ELISA (IgG) ELISA Units per CBER comments: SCR is defined as proportion of participants who achieve seroconversion \geq 4-fold increase from baseline in IgG GMEUs at Day 29 if the baseline value is equal to or above LLOQ or at least 4-fold fold rise from LLOQ if the baseline value is lower than LLOQ
Section 7.2.3	Clarify SCR definition for hACE2 titers per CBER comments: SCR is defined as proportion of participants who achieve seroconversion \geq 4-fold increase from baseline in hACE2 titers at Day 29 if the baseline value is equal to or above LLOQ or at least 4-fold fold rise from LLOQ if the baseline value is lower than LLOQ
Section 7.3.1	Clarify the grading of solicited AEs, especially Grade 4 for redness and swelling
Section 7.3.2	Delete the period of Days 29 – 181
Table 11	Add the missing 3 rd to 6 th footnotes
References	Add one missing reference (FDA 2007) for Table 10 and three missing references (Ferreira 2018, Adler 2015, and Gargano 2021) for Table 11.

SAP Version 4.0, 22 August 2023 (revised from Version 3.0, 22 May 2023)

The following is a summary of the changes made to this SAP.

Location of Change	Change/Modification in Version 4.0
Section 1.2, 7.1, 7.2 and 11	Change the terminology from GMFR _{312/307} to GMR _{312/307}
Section 7.2.1	Add the statements of the conversion from the values of Pseudovirus-based Nab response (Wuhan) in ID50 tested by Monogram for Study 2019nCoV-307 and those tested by NVX CI for Study 2019nCoV-312 to the values in the standard unit of IU/mL. Clarify the summary of Pseudovirus-based Nab response per Wuhan and Omicron BA.5 strain since Pseudovirus-based Nab response per Omicron BA.5 was not tested in Study 2019nCoV-307.
Section 7.2.2	Clarify the summary of IgG per Wuhan and Omicron BA.5 strain
Section 7.2.3	Clarify the summary of hACE2 per Wuhan and Omicron BA.5 strain due to no data of hACE2 per Omicron BA.5 strain from Study 2019nCoV-307.
Section 12 Reference	Add one Monogram report as the reference of the conversion factor (0.1458) Add one NVX CI PNA validation report as the reference of the conversion factor (0.214).

TABLE OF CONTENTS

APPROVAL SIGNATURE PAGE.....	2
SAP CHANGE HISTORY	4
TABLE OF CONTENTS.....	6
LIST OF TABLES.....	8
LIST OF FIGURES	8
LIST OF ABBREVIATIONS	9
1 INTRODUCTION.....	11
1.1 Study Design	12
1.2 Sample Size Rationale	13
1.3 Scope of the Analysis Plan	13
2 OBJECTIVES AND ENDPOINTS	14
3 ANALYSIS SUBSETS	16

Table 10:	Modified FDA Toxicity Grading Scale for Clinical Abnormalities (Local and General Systemic Reactogenicity)	46
Table 11:	Case Definitions of Probable and Confirmed Myocarditis, Pericarditis, and Myopericarditis	47

LIST OF FIGURES

Figure 1:	Flow Diagram of Study 2019nCoV-312.....	12
Figure 2:	Geometric Mean Titer and Seroconversion Rate Comparison between 2019nCoV-312 and Study 2019nCoV-307	24

LIST OF ABBREVIATIONS

Abbreviation	Definition
AE	Adverse event
AESI	Adverse event of special interest
ANCA	Anti-neutrophil cytoplasmic antibody
ARDS	Acute respiratory distress syndrome
ATC	Anatomical therapeutic chemical
BMI	Body mass index
CI	Clinical Immunology
CI	Confidence interval
COVID-19	Coronavirus disease 2019
CRO	Clinical research organization
CSR	Clinical Study Report
DAIDS	Division of AIDS
Division of AIDS	Division of AIDS
ECG	Electrocardiogram
eCRF	Electronic case report form
EDC	Electronic data capture
ELISA	Enzyme-linked immunosorbent assay
EOS	End of Study
ELISA	ELISA
FAS	Full Analysis Set
FDA	United States Food and Drug Administration
GCP	Good Clinical Practice
GMEU	Geometric mean ELISA unit
GMFR	Geometric mean fold rise
GMT	Geometric mean titer
hACE2	Human angiotensin-converting enzyme 2
HEENT	head nose ears and throat
ICF	Informed consent form
ICH	International Council for Harmonisation of Technical Requirements for Pharmaceuticals for Human Use
IgG	Immunoglobulin G
IRB	Institutional Review Board
MAAE	Medically attended adverse event
MedDRA	Medical Dictionary for Regulatory Activities
MN ₅₀	Microneutralization assay with an inhibitory concentration of 50%
OTC	Over the counter
PCR	Polymerase chain reaction

Abbreviation	Definition
PIMMC	Potential immune-mediated medical conditions
PP	Per-Protocol
PT	Preferred term
Rs	Recombinant spike
S	Spike (protein)
SAE	Serious adverse event
SARS-CoV	Severe acute respiratory syndrome coronavirus
SARS-CoV-2	Severe acute respiratory syndrome coronavirus 2
SCR	Seroconversion rate
SII	Serum Institute of India
SOC	System organ class
SOE	Schedule of Events
SOP	Standard Operating Procedure
TEAE	Treatment-emergent adverse event
TGS	Toxicity grading scale
US	United States

1 INTRODUCTION

Novavax, Inc. has developed a recombinant spike protein vaccine adjuvanted with the saponin-based Matrix M adjuvant for the prevention of disease caused by SARS-CoV-2 (NVX-CoV2373). NVX-CoV2373 is the ancestral strain SARS-CoV-2 rS nanoparticle vaccine construct adjuvanted with Matrix-M™ adjuvant that is authorized for the active immunization for the prevention of mild, moderate, and severe COVID-19 caused by SARS-CoV-2 in adults 18 years of age and older and adolescents 12 – 17 years of age. The investigational products used in this study are manufactured by Serum Institute of India (SII) through a partnership with Novavax.

Supportive clinical data are available via studies conducted using Novavax manufactured SARS-CoV-2 rS products. The clinical development program for Novavax's SARS-CoV-2 rS with Matrix-M adjuvant comprises 4 ongoing clinical studies: a Phase 1-2 study of SARS-CoV-2 rS with or without Matrix-M adjuvant in healthy adult participants 18 to 59 years of age (Study 2019nCoV-101 – Part 1) and SARS-CoV-2 rS with Matrix-M adjuvant in healthy adult participants 18 to 84 years of age (Study 2019nCoV-101 – Part 2); a Phase 2a/b study of SARS-CoV-2 rS with Matrix-M adjuvant in healthy adult participants 18 to 84 years of age living without human immunodeficiency virus (HIV) and medically stable adult participants 18 to 64 years of age living with HIV (Study 2019nCoV-501); and 2 Phase 3 studies in healthy and medically stable adult participants \geq 18 years of age and adolescent subjects 12 to $<$ 18 years of age (Study 2019nCoV-301) and 18 to 84 years of age (Study 2019nCoV-302). Additionally, Study 2019nCoV-307, which confirmed the lot-to-lot consistency of three manufacturing lots also looked at the effect of homologous and heterologous boosting with NVX-CoV2373 in adults \geq 18 – 49 years of age and forms the basis for this study and its enrollment population.

Study 307 is a phase 3 study that compared the immunogenicity and safety of 3 lots of NVX-CoV2373 in adults to demonstrate the consistency of effect among the 3 manufacturing lots of drug product. We also explored the immune response following heterologous and homologous boosting with respect to Wuhan and Omicron strains of COVID-19. NVX-CoV2373 showed equivalent immunogenicity across manufacturing lots, as measured by IgG and Nab responses. No new safety signals were identified. NVX-CoV2373 was also immunogenic regardless of whether it was used as a first booster or later booster dose, and whether it followed earlier doses of NVX-CoV2373 or other authorized vaccines. Additionally, it displayed immunogenicity against all 3 tested variants of SARS-CoV-2 rS. Participants in Study 307 who received a primary series of an mRNA vaccine were invited to participate in this study.

The purpose of this study is to assess immunogenicity and safety of ancestral strain NVX-CoV2373 and, possibly, an updated Novavax vaccine based on recent variant(s), when used as a second or subsequent booster dose in individuals who previously received primary vaccine series of licensed mRNA with or without a subsequent mRNA booster dose followed by one booster with ancestral strain NVX-CoV2373 vaccine who were 18 to 49 years of age at the time of vaccination in Study 2019nCoV-307.

1.1 Study Design

This is a Phase 3 study assessing the immunogenicity and safety of Novavax vaccine with Matrix-M™ adjuvant (NVX-CoV2373) as a booster dose following primary vaccination with authorized/approved mRNA vaccines (with or without subsequent mRNA booster) and one booster dose of NVX-CoV2373. The study will enroll up to 300 previously vaccinated and boosted adults 18 to 49 years of age at the time of vaccination in Study 2019nCoV-307 (Table 1).

Participants will be recruited from individuals who previously participated in Study 2019nCoV-307 (received mRNA vaccine priming with or without a subsequent mRNA booster and an NVX-CoV2373 booster dose in the 307 study).

Table 1: Study Vaccinations

[figure not shown]
Vaccine	Age (years)*	Baseline Serostatus	Number of doses	Number of participants	Dose (antigen/Matrix-M adjuvant)
Ancestral strain NVX-CoV2373	18 – 49	Previously vaccinated	1	100 – 150	5 µg / 50 µg
Updated Novavax COVID-19 Vaccine based on recent variant(s)	18 – 49	Previously vaccinated	1	100 – 150	5 µg / 50 µg

*Age at time of enrollment in Study 307

Participants will receive 1 dose of study vaccine, given on Day 1, at a dose level of 5 µg of rS antigen with 50 µg of Matrix-M adjuvant.

All participants will remain on study for immunogenicity at Day 29 and safety data collection through 180 days following the vaccination (Figure 1).

Figure 1: Flow Diagram of Study 2019nCoV-312

1.2 Sample Size Rationale

The sample size and power are driven by the primary endpoint (ie, Nab responses to ancestral strain Novavax vaccine administered as a second (or subsequent) booster after licensed mRNA vaccines and a first ancestral strain Novavax vaccine booster).

MN₅₀ data from Novavax's study 2019nCoV-301 of around 240 adult participants who received the SARS-CoV-2 rS vaccine on Day 0 and Day 21 in the initial period of primary series or crossover period then received boost dose at Day 0 in the booster period exhibited an 80% confidence upper bound of standard deviation of MN₅₀ GMR between 28 days after the third active (booster) dose and 14 days after 2nd active dose in log₁₀ scale of 0.61.

The sample size (Table 2) is based on providing at least 90% power to conclude non-inferiority on Nab titers given the null hypothesis (Section 7.1) of GMR_{312/307} defined as the ratio of GMT₃₁₂ to GMT₃₀₇ ≤ 0.67 . Here, GMT₃₁₂ is Nab GMT at Day 29 from 2019nCoV-312 and GMT₃₀₇ is Nab GMT at Day 29 from 2019nCoV-307. It is anticipated that these estimates will be equally applicable in the event that a different assay of Nab titers is used for this study.

Table 2: Summary of Sample Size

GMR	N
1.0	129
1.1	85
1.2	62
1.3	49
1.4	40
1.5	34

Note: GMR is defined as the ratio of Day 29 GMT in 2019nCoV-312 to Day 29 GMT in 2019nCoV-307; N is the count of participants.

1.3 Scope of the Analysis Plan

This statistical analysis plan (SAP) provides a detailed outline of the immunogenicity and safety analyses in accordance with Study Protocol 2019nCoV-312 Version 1.0, dated 10 February 2023 (Study 312 Protocol), and will address the analysis presentation of interim analysis (or called Day 29 primary analysis) review of all immunogenicity and safety data through Day 29. This SAP will also address the analysis presentation of final analysis review of all safety data through EoS.

Any deviations from this SAP will be described and justified in the Clinical Study Report (CSR).

All data analyses and generation of TLFs will be performed using SAS 9.4[®] or higher.

2 OBJECTIVES AND ENDPOINTS

An overview of all study objectives and endpoints is provided in [Table 3](#).

Table 3: Study 2019nCoV-312 Objectives and Endpoints

	Objectives	Endpoints
Primary	To characterize the Nab responses (geometric mean titers, GMTs) to ancestral strain Novavax vaccine administered as a second (or subsequent) booster after licensed mRNA vaccines and a first ancestral strain Novavax vaccine booster	
• Nab GMTs to the ancestral strain SARS-CoV-2 at Day 29. Non-inferiority will be demonstrated if the lower-bound (LB) of the 95% CIs for the ratio of Nab GMT at Day 29 between the two booster periods is > 0.67.• If non-inferiority is demonstrated, results will be tested for superiority, defined as the LB of 95% CIs for the ratio of Nab GMT at Day 29 > 1.0.
Secondary	To further characterize the Nab responses (seroconversion rate, SCR) to ancestral strain Novavax vaccine administered as a second (or subsequent) booster after licensed mRNA vaccines and a first ancestral strain Novavax vaccine booster.	Proportion of participants who achieve seroconversion (≥ 4 -fold increase from baseline) in neutralization antibody titers to the SARS-CoV-2 at Day 29 compared with results of the same measurements in participants who received their first ancestral strain Novavax vaccine booster after mRNA vaccination in Study 2019nCoV-307. Non-inferiority will be demonstrated if the LB of the 95% exact CIs for the difference of SCRs in Nab titers is higher than -10%
	To demonstrate the noninferior immunogenicity of Novavax vaccine as a second (or subsequent) booster vs as a first booster of ancestral strain Novavax vaccine boost following mRNA vaccines.	
• IgG geometric mean enzyme-linked immunoassay (ELISA) unit concentrations (GMEU/mL) to the SARS-CoV-2 ancestral strain spike protein at Day 29; Non-inferiority will be demonstrated if the lower-bound (LB) of the 95% CIs for the ratio of IgG GMEU at Day 29 between the two booster periods is > 0.67.• If non-inferiority is demonstrated, results will be tested for superiority, defined as a lower 95% confidence interval of GMEU ratio > 1.0.• Proportion of participants who achieve seroconversion (≥ 4-fold increase from baseline) in IgG concentrations to the SARS-CoV-2 ancestral strain spike protein at Day 29 compared with results of the same measurements in participants who received their first ancestral strain Novavax vaccine booster after mRNA vaccination in Study 2019nCoV-307. Non-inferiority will be demonstrated if the LB of the 95% exact CIs for the difference of SCRs in IgG ELISA unit is higher than -10%.
	To characterize the cross-reaction of neutralizing and IgG antibodies induced by the ancestral strain Novavax vaccine to more recent SARS-CoV-2 variants and any other variants for which appropriate assays are available.	Post-booster neutralizing GMTs and IgG GMEUs compared with post-first booster results from Study 307.

Table 3: Study 2019nCoV-312 Objectives and Endpoints

	Objectives	Endpoints
Secondary (cont.)	To further characterize antibody responses in a human angiotensin-converting enzyme 2 (hACE2) receptor binding inhibition assay to the SARS-CoV-2 ancestral strain spike protein using the same calculations and comparison group as noted above for neutralizing and IgG antibodies.	Seroresponse data from Study 307 participants enrolled to the second treatment group of this study to receive an updated Novavax vaccine based on recent variant will be assayed using the same assays as described above. hACE2 antibodies post-updated booster will be compared to those post-ancestral strain boosters and will be analyzed in the same manner specifically to assess reactivity with the ancestral strain virus/spike protein and with recent variant virus/spike protein.
	To describe the overall safety of ancestral strain and updated (if administered) Novavax vaccine(s) administered as a second (or subsequent) booster following licensed mRNA vaccines and a first ancestral strain Novavax vaccine booster.	
• Incidence, duration and severity of solicited adverse reactions in the 7 days following study vaccination.• Incidence, duration, severity, and relationship of medically attended adverse events (MAAEs) and adverse events of special interest (AESIs), (including myocarditis and/or pericarditis) through Day 180 after the vaccine dose.• Incidence and relationship of serious adverse events (SAEs) through Day 180 after the vaccine dose.
Exploratory	To utilize additional assays (current or to be developed) to best characterize the immune response for future vaccine development needs, including testing against emerging variants of SARS-CoV-2.	Additional endpoints to evaluate immune responses may be developed based on the assays used.

3 ANALYSIS SUBSETS

The following analysis sets are identified for analysis.

3.1 Selected Participants Analysis Set

The Selected Participants Analysis Set will include all participants who are enrolled, regardless of whether they received any study vaccine. The Selected Participants Analysis Set will be used for participant disposition summaries and will be analyzed according to the treatment as enrolled.

3.2 Full Analysis Set

The full analysis set (FAS) will include all participants who are enrolled and received a dose of study vaccine, regardless of protocol violations or missing data. Participants in the FAS will be analyzed according to the vaccine group as enrolled. Please note, the analysis per FAS will not be performed due to the change of enrollment procedure, that is, subjects to be dosed with ancestral strain NVX-CoV2373 are enrolled first and subjects to be dosed with updated Novavax COVID-19 Vaccine based on recent variant(s) are enrolled afterward.

3.3 Safety Analysis Set

The Safety Analysis Set will include all participants who provide consent, are enrolled, and receive 1 dose of study vaccine. Participants in the Safety Analysis Set will be analyzed as actually treated. The Safety Analysis set will be used for all safety analyses.

3.4 Per-Protocol Analysis Set

The first Per-Protocol Analysis Set (PP1) will include all participants who receive the study vaccine according to the protocol with no receipt of another COVID vaccine (authorized or approved) after Day 1 vaccination, have serology results for baseline and Day 29 available after the vaccination, are PCR negative at baseline for SARS-CoV-2, do not report SARS-CoV-2 infection through Day 29 blood draw, and have no major protocol violations that are considered clinically relevant to impact immunogenicity response as determined by Novavax prior to database lock. This population will reflect the general population many of whom, three years into the pandemic, have experienced SARS-CoV-2 infection, and the immunogenicity measured after study vaccine may reflect “hybrid immunity”. Negative anti-NP result at baseline is not required. Participants with missing anti-NP at baseline will be included in the PP1.

The second Per-Protocol Analysis Set (PP2), intended to represent individuals who have not experienced natural SARS-CoV-2 infection, is defined similarly to PP1 except that it requires a negative baseline anti-N result. Participants with missing baseline anti-N results will be excluded from second Per-Protocol Analysis Set (PP2).

Within the two PP Analysis Sets there are 3 subsets defined separately: Anti-S Protein IgG Serology Subset, Neutralization Assay Subset, and the hACE2 Receptor-binding Inhibition Assay Subset.

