3.5.2 Major Protocol Deviations Assessment

Protocol deviations deemed to indicate clear violations of GCP and/or subject consent; or to have a likely effect on the primary and secondary immunogenicity outcomes will exclude those participants from both PP analysis sets (PP1 and PP2). This determination will be made by the NOVAVAX Clinical Lead prior to database freeze or lock.

When interim analysis (Day 29 primary analysis) DB freezes or Day 181 final analysis DB locks, Syneos will assess protocol deviations and create a consensus final protocol deviations assessment file. NOVAVAX team will determine whether PDs are major and make the final decision of which participants will be excluded from the PP analysis based on the PD listing from Syneos.

In general, inclusion/exclusion criteria failure, receipt of prohibited therapies, receipt of another COVID vaccine (authorized or approved), missed blood draw and laboratory samples obtained sufficiently outside visit windows to likely impact the result will be deemed “major” deviations relevant for analysis. Criteria for this determination will be established prior to review of PDs. Any positive PCR or anti-NP result obtained at baseline Day 1 is not exclusionary and will not be considered a major PD.

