4 PARTICIPANT DISPOSITION

The number of participants consented, enrolled, and vaccinated will be presented by the study vaccine group for all participants in the Selected Participants Analysis Set.

The number (percentage) of participants in the Selected Participants Analysis Set, Safety Analysis Set, and both PP Analysis Sets who have completed the study from Day 1 through Day 29 for the interim analysis (Day 29 primary analysis) and who have completed the study from Day 1 through EoS for the final analysis will be summarized by the study vaccine group.

The number (percentage) of participants in the Safety Analysis Set who discontinue the study prior to Day 29/EoS and the reason for study discontinuation (eg, AE, death, lost to follow-up, physician/investigator decision, sponsor decision, withdrawal of consent, etc.) will be presented by the study vaccine group. A listing of all participants discontinued from the study will be presented, including the reason for discontinuation and day of last study contact. Day of last study contact will be calculated as follows: date of study discontinuation minus date of Day 1 vaccination + 1. A listing of all screened participants who failed the inclusion/exclusion criteria will also be provided.

The number (percentage) of participants in the Safety Analysis Set with major protocol deviations recorded prior to Day 29/throughout the study will be summarized by the study vaccine group and protocol deviation category (according to the Protocol Deviations and Site Level Non-compliances provided by Syneos and confirmation by NOVAVAX). A listing of all participants with one or more major protocol deviations will also be provided and will include study vaccine group, study day associated with the deviation relative to Day 1, protocol deviation category, and a description of the deviation as recorded by the site.

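### The per-protocol rule on another COVID vaccine has no end date, so a vaccine given after the Day 29 draw could remove a valid Day 29 pair from PP1 and PP2

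*SAP*

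**What the plan says.** SAP 3.4 defines PP1 by a list of separate conditions. One is that participants received the study vaccine "with no receipt of another COVID vaccine (authorized or approved) after Day 1 vaccination". Another, in the same sentence, is that they "do not report SARS-CoV-2 infection through Day 29 blood draw". The first has no closing date; the second closes at the Day 29 draw. PP2 "is defined similarly to PP1 except that it requires a negative baseline anti-N result", so it inherits the open-ended vaccine condition.

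SAP 3.5.2 lists "receipt of another COVID vaccine (authorized or approved), missed blood draw" among the deviations that will generally count as major, again without a time limit. It lists use of prohibited therapies separately, and Protocol 7.3.1 prohibits any COVID-19 vaccine for the whole study. On timing, SAP 3.5.2 says: "When interim analysis (Day 29 primary analysis) DB freezes or Day 181 final analysis DB locks, Syneos will assess protocol deviations".

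The Schedule of Events has immunogenicity draws at Day 1 and Day 29 only. Protocol 7.3 has sites record COVID vaccines from Day 30 to end of study, so later receipt will be in the data. SAP 3.2 states that no FAS analysis will be done, and SAP 7.2 bases immunogenicity on PP1 and PP2.

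**The concern.** A vaccine given after the Day 29 sample cannot change the titer in that sample. Read literally, SAP 3.4 still removes the participant from both sets used for the primary endpoint. That costs a valid 312/307 pair and makes inclusion depend on behaviour after the endpoint was measured. Whether a pair is lost can also depend on how long the participant has been followed when the database is frozen. With the FAS analysis dropped, no planned immunogenicity result would show whether the exclusions mattered.

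**Working it through.** **Can the rule take effect before the primary analysis?** SAP 9 runs the first Day 29 analysis once the ancestral group's data through Day 29 are entered, reviewed and queried. Participants enrolled early will be past their own Day 29 by then. SAP 9 and Protocol 9.4 allow the two interim analyses to be combined, and SAP 3.2 says the updated-vaccine group is enrolled after the ancestral group. If they are combined, ancestral-group participants could be well past Day 29 at the freeze. So there is an interval, of a length the documents do not give, in which a later vaccine could be on record.

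**Does other wording close the gap?** In SAP 3.4 the qualifier about clinical relevance to the immune response attaches to major protocol violations, not to the vaccine condition, which stands alone. SAP 3.5.2 sets its own test: clear breaches of GCP or consent, or a likely effect on the immunogenicity outcomes. A vaccine given after the draw has no such effect, so the test in 3.5.2 and the condition in 3.4 point different ways. The PP definition in Protocol 9.2.4 has no separate vaccine condition.

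**Does membership matter again later?** SAP 4 summarises both PP sets by participants "who have completed the study from Day 1 through EoS for the final analysis". The PP counts shown then could differ from those at the freeze.

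**Size.** Inputs: SD of the log10 paired ratio 0.61 and Table 2 (SAP 1.2); margin 0.67 (SAP 7.1); lower limit of a two-sided 95% CI from a paired t (SAP 7.2.1), so one-sided alpha 0.025; planned ancestral group 100–150 (SAP Table 1).

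Power = 1 − F(t(0.975, n−1); n−1, δ), where F is the noncentral t distribution function and δ = √n × [log10(GMR) − log10(margin)] / 0.61.

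The plan's own figures come first. With a margin of 2/3 this gives 129, 85, 62, 49, 40 and 34 for GMR 1.0 to 1.5, which is Table 2 exactly. With the stated 0.67 it gives 132, 87, 63, 50, 41 and 34, and 89.5% power at n = 129. The half point below 90% comes from rounding of the margin, not from the rule discussed here.

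At GMR 1.0 and margin 0.67, −log10(0.67) = 0.1739, 0.1739/0.61 = 0.2851, and δ = 0.2851 × √n. The share lost is **assumed**, and the remaining pairs are rounded down:

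| Assumed loss | Pairs from 129 | δ | Power | Pairs from 150 | δ | Power |
|---|---|---|---|---|---|---|
| 0% | 129 | 3.238 | 89.5% | 150 | 3.492 | 93.4% |
| 5% | 122 | 3.149 | 87.8% | 142 | 3.398 | 92.1% |
| 10% | 116 | 3.071 | 86.1% | 135 | 3.313 | 90.8% |
| 20% | 103 | 2.894 | 81.8% | 120 | 3.123 | 87.2% |

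From the low end of planned enrolment, 100 pairs, power goes from 80.6% to 78.5%, 76.3% or 71.2%. GMR 1.0 is the least favourable row of Table 2. At GMR 1.1 the table asks for 85, which even 103 pairs exceed.

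**The case against.** The strongest reply is that the Day 29 analysis is limited in scope. SAP 1.3 describes it as a "review of all immunogenicity and safety data through Day 29", and SAP 4 counts major deviations recorded before Day 29 or throughout the study, which reads most naturally as one window per analysis. On that reading a vaccine given on, say, Day 60 would not be used at the primary analysis. SAP 3.5.2 also introduces its list as a general rule and has the criteria fixed before deviations are reviewed, which leaves room not to exclude. These points stand, and they are why the loss is stated as possible, not certain. They do not put an end date on the separate condition in SAP 3.4.

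It is also fair to say that COVID vaccines are prohibited throughout the study, so the 5–20% scenarios assume that share departs from the protocol in the interval before the freeze. Nothing in the documents supports or refutes such a rate.

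A reader might go further and infer that two data cuts will yield two different primary GMRs. The documents do not support that. SAP 1.3 and 9 and Protocol 9.5 describe the final analysis as one of safety data, and each group's immunogenicity is scheduled once. A reader might likewise infer a bias in a known direction, because later vaccination could follow health status or perceived response. The documents give no evidence on this.

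**Conclusion.** The point holds as a gap in the wording of the only planned immunogenicity sets. As written, SAP 3.4 could discard valid Day 29 pairs for an event after the endpoint, and it conflicts with the exclusion test in SAP 3.5.2. The cases at risk are participants vaccinated between their Day 29 draw and the freeze: early enrolees, or ancestral-group participants if the interims are combined. Confidence is high on the wording and low on the impact. At an assumed 5% loss the cost at GMR 1.0 is 1.7 points of power from 129 pairs (89.5 − 87.8) and 1.3 from 150 (93.4 − 92.1). At 20% it is 7.7 and 6.2 points. What may change between freeze and lock is PP membership and the reported PP counts, not a planned GMR.

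**What to change.** In SAP 3.4, change the PP1 condition, which PP2 inherits, to: *no receipt of another COVID-19 vaccine from Day 1 vaccination through the Day 29 blood draw*.

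In SAP 3.5.2, limit exclusion from the PP sets to the same window for both routes: the item on receiving another COVID vaccine, and the item on prohibited therapies where the therapy is a COVID vaccine. If only the first is changed, a later vaccine could still exclude a participant through the second, because Protocol 7.3.1 applies for the whole study.

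Later receipt remains a reported protocol deviation and the protocol's prohibition is unchanged. The cost is a short SAP amendment to two sections, made before deviations are reviewed for the freeze. No visit, sample or data collection changes.
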